Primary Endpoint	
TLF through 30-day, tested for non-inferiority of Absorb BVS to XIENCE.
 
• This analysis will consist of ~2600 subjects in ABSORB IV.
Powered Secondary Endpoints	
1. TLF through 1 year, tested for non-inferiority of Absorb BVS to XIENCE.2. Angina Powered Secondary Endpoint: The percentage of patients who experienced angina within 1 year, tested first for non-inferiority of Absorb BVS to XIENCE with reflex testing to superiority.
• Angina is defined as any angina or angina equivalent symptoms determined by the physician and/or research coordinator after interview of the patient, and as adjudicated by a clinical events committee (CEC).• This analysis will exclude angina or angina equivalent symptoms that occurred following the index procedure through hospital discharge or 7 days, whichever occurs first.
○ For subjects who receive a planned staged procedure to treat one or more target lesions, the analysis will exclude angina or angina equivalent symptoms that occurred following the original index procedure through hospital discharge or 7 days after the final procedure, whichever occurs first.

	These analysis will consist of ~2600 subjects in ABSORB IV
Patient Reported Outcome (PRO) Informational Endpoints	
Patient-reported outcomes (PRO) are informational endpoints to assess Health-Related Quality of Life. PRO assessments will be conducted at baseline, 1 and 6 months, and at 1, 3 and 5 years. The following questionnaires will be used in this study:
 
 • Seattle Angina Questionnaire-7 (SAQ-7) to assess disease-specific Quality of Life • EuroQoL 5D (EQ-5D) survey to assess overall health status 
(Note: PRO endpoints will be evaluated in the ~2600 subjects of ABSORB IV)
 
The PROs will be analyzed to evaluate the relationship between quality of life and cardiovascular events that occurred post-PCI and to substantiate the clinical impact of the angina events identified in the trial.

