Health Economics Informational Endpoints	The primary analysis is to compare the resource utilization and costs between the two treatment groups at 1, 2 and 3 years. If the rates of angina, hospitalizations or revascularizations are different between the two arms, a cost effectiveness analysis will be performed evaluating the cost of angina, hospitalizations or revascularizations avoided.
Subject Enrollment, Randomization and Registration	
 • Subjects are considered enrolled in ABSORB IV after signing the Informed Consent. • Subjects are considered randomized in ABSORB IV after the interactive voice response system (IVRS) has been called and a device (Absorb BVS or XIENCE) has been assigned. • Subjects are considered registered in the ABSORB IV upon randomization. • Enrolled subjects not randomized in the trial will be considered screen failures and will not be followed.
Clinical Follow-Up	
All registered subjects in ABSORB IV will receive the following clinical follow-up:
 
 ○ 30 ± 7 days follow-up telephone contact/office visit ○ 90 ± 14 days follow-up telephone contact/office visit

	
 ○ 180 ± 28 days follow-up telephone contact/office visit ○ 270 ± 28 days follow-up telephone contact/office visit ○ 1 year ± 28 days follow-up telephone contact/office visit ○ 2 years ± 28 days follow-up telephone contact/office visit ○ 3 years ± 28 days follow-up telephone contact/office visit ○ 4 years ± 28 days follow-up telephone contact/office visit ○ 5 years ± 28 days follow-up telephone contact/office visit

Patient Reported Outcome (PRO) Assessments
	
All registered subjects of ABSORB IV will receive the following PRO assessments:
 
 ○ Baseline: SAQ-7, EQ-5D ○ 30 ± 7 days: SAQ-7, EQ-5D ○ 180 ± 28 days: SAQ-7, EQ-5D ○ 1 year ± 28 days: SAQ-7, EQ-5D ○ SAQ-7, EQ-5D will also be administered to all registered subjects at 3 and 5 years (± 28 days) visits.

Primary Analysis Sample Size Justification
	

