1. INTRODUCTION

The ABSORB IV Randomized Controlled Trial (RCT) is designed to continue to evaluate the safety and effectiveness as well as the potential short and long-term benefits of Abbott Vascular Absorb™ Bioresorbable Vascular Scaffold (BVS) System⁴⁹, and the Absorb GT1™ BVS System, as compared to the commercially approved, control stent XIENCE. In the subsequent sections of this protocol, the term “Absorb BVS” will be used to represent both Absorb™ BVS and Absorb GT1™ BVS.

ABSORB IV is a prospective, randomized (1:1 Absorb BVS to XIENCE), single-blind, multi-center trial, registering approximately 2600 subjects from approximately 140 sites⁵⁰ in the United States and outside the United States. The primary objective of ABSORB IV is to evaluate 30-day and long-term clinical outcomes of the Absorb BVS compared to XIENCE in the treatment of subjects with ischemic heart disease caused by up to three *de novo* native coronary artery lesions in a maximum of two epicardial vessels, with a maximum of two lesions per epicardial vessel. The primary endpoint data of TLF through 30-day, tested for non-inferiority of Absorb BVS to XIENCE, will be tested on the ~2600 ABSORB IV subjects. The secondary objectives of ABSORB IV will be to evaluate TLF at 1-year and the incidence of angina occurring within 1 year, with treatment of Absorb BVS compared to XIENCE. The ABSORB IV protocol trial will compare patient reported outcomes, resource utilizations and costs between the Absorb BVS and XIENCE arms. These analyses will be based on all ~2600 subjects of ABSORB IV. The original design of the ABSORB IV trial also included an imaging ischemia sub-study aimed at providing the physiological and mechanistic evaluation of whether PCI treatment with Absorb BVS compared to XIENCE results in differences in myocardial ischemia in the early post-procedural period, and at 14 months and 62 months. However, this sub-study had to be stopped due to very slow enrollment (see **Section 12** for more details).

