5.4.2 Health Economics

During the course of the trial, the Sponsor (or the health economic core laboratory) will collect health economic data. The data may include billing information and claims data for the index hospitalization and for subsequent hospitalizations during the follow-up period, for sites located in the United States only. Patients will be asked to provide consent to access billing information for the purposes of conducting economic analysis of the trial.

Additional information regarding medical resource utilization may also be collected throughout the trial, including but not limited to: laboratory services, diagnostic procedures, or pharmacy records.

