10.4.5 Informational Endpoint Analyses

Details on informational endpoint analyses can be found in the SAP.

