1.5.2.2 Powered Secondary Endpoint #2: Angina through 1 year

[REDACTED]

[REDACTED]

The hypothesis test is designed to show non-inferiority of Absorb BVS to XIENCE for angina within 1 year with a one-sided alpha of 0.025. [REDACTED]

[REDACTED]

[REDACTED]

[REDACTED]

[REDACTED]

The power calculation for the powered secondary endpoint of angina within 1 year is based on the following assumptions:

[REDACTED]

- One-sided alpha: 2.5%
- Non-inferiority margin (Δ_{ANGINA}): 7%
- Randomization ratio (ABSORB IV): 1 (Absorb BVS arm) : 1 (XIENCE arm)

[REDACTED]

With the effective sample size 2470 (Absorb: 1235, XIENCE: 1235) at 1 year, the study has approximately 99% power to demonstrate non-inferiority of Absorb BVS to XIENCE using Farrington and Manning test¹.

[REDACTED]

[REDACTED]

[REDACTED]

[REDACTED]

[REDACTED]

[REDACTED]

[REDACTED]

[REDACTED]

[REDACTED]

[REDACTED]

[REDACTED]

[REDACTED]

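### ABSORB IV runs its cost-effectiveness analysis only if event rates turn out different, so the cost per event avoided is selected on the trial's own result

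*Protocol*

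**What the plan says.** The rule is in the ABSORB IV Protocol Summary, in the row on health economics informational endpoints. It begins with an analysis that carries no condition: "The primary analysis is to compare the resource utilization and costs between the two treatment groups at 1, 2 and 3 years". It then adds a second step: "If the rates of angina, hospitalizations or revascularizations are different between the two arms, a cost effectiveness analysis will be performed", this being an analysis "evaluating the cost of angina, hospitalizations or revascularizations avoided". No significance level, minimum size, time point or direction is attached to the trigger, and a difference on any one of the three outcomes is enough.

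Other places bear on this:

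- The ABSORB IV Introduction says the trial "will compare patient reported outcomes, resource utilizations and costs between the Absorb BVS and XIENCE arms", again without a condition. It does not mention cost-effectiveness.
- ABSORB IV section 5.4.2 (Health Economics) describes the data. Billing and claims data are "for sites located in the United States only".
- ABSORB IV section 5.3 lists three categories of rehospitalization and several of revascularization (target lesion, target vessel, each ischemia-driven or not, and all coronary). The summary does not say which of these opens the gate.
- ABSORB IV section 10.4.5 defers: "Details on informational endpoint analyses can be found in the SAP". The visible SAP has no health-economics text, and much of it is blacked out.
- EQ-5D, a "survey to assess overall health status", is scheduled at baseline, 30 and 180 days, and 1, 3 and 5 years.

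**The concern.** A cost per event avoided has the between-arm difference in events as its denominator. If the ratio is produced only when that difference has passed some test, the difference reported is on average further from zero than the truth. A denominator that is too large makes each avoided event look too cheap. If the gate stays shut, no ratio is produced, although incremental cost with a small and uncertain effect still informs a judgement of value.

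A shut gate is a realistic outcome here. Angina is tested first for non-inferiority, with a 7-point margin (SAP section 1.5.2.2), so a small or null angina difference is something the design allows for. A difference that is not significant is also not the same as no effect.

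**Working it through.** The plan gives no threshold, power or sample size for this trigger, so there is no figure of its own to reproduce. What follows illustrates the size of the effect under stated assumptions.

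**Inputs**

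- 1235 per arm at 1 year, from SAP section 1.5.2.2: "With the effective sample size 2470 (Absorb: 1235, XIENCE: 1235) at 1 year".
- Angina rate: the planning rate is redacted. I assume 16% to 27.9%, the two background rates in ABSORB IV section 2.2, with 20.8% as a point inside that range. The same rate is used in both arms for the standard error.
- Trigger: two-sided p<0.05 (assumption).

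**Chance of opening with no true difference**

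- Three independent outcomes, one time point: 1 − 0.95³ = 0.143.
- Three equally correlated outcomes, by simulation: 13.6% at correlation 0.3, 12.5% at 0.5, 9.9% at 0.8.
- Three outcomes at three time points: 1 − 0.95⁹ = 0.370 if all nine were independent. This is an upper bound, since repeated looks at the same outcome are correlated.

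**Average angina difference once an angina-only gate has opened**

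Standard error: SE = √(2p(1−p)/1235). For a true difference d, the probability of a significant result in the true direction is P = 1 − Φ(1.96 − d/SE), and the mean estimate given that result is d + SE·φ(1.96 − d/SE)/P.

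At p = 0.208 and d = 2 points: SE = 1.63 points, d/SE = 1.22, P = 0.23, φ(0.735) = 0.304. The mean is 2 + 1.63 × 0.304/0.231 = 4.15 points. Including the rare significant result in the wrong direction gives 4.13.

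| Assumed rate | SE (points) | Chance of passing, d = 2 | Mean estimate, d = 2 | Mean estimate, d = 5 |
|---|---|---|---|---|
| 16% | 1.47 | 27% | 3.8 | 5.2 |
| 20.8% | 1.63 | 23% | 4.1 | 5.4 |
| 27.9% | 1.80 | 20% | 4.5 | 5.7 |

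At d = 10 points there is no material inflation.

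**Average angina difference under the three-outcome gate as written**

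Suppose the other two outcomes are independent of angina and have no true difference. They open the gate on their own with probability q = 1 − 0.95² = 0.0975. At p = 0.208 and d = 2:

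- P(gate opens) = 0.232 + 0.768 × 0.0975 = 0.307.
- Mean estimate = [0.232 × 4.13 + 0.0975 × (2 − 0.232 × 4.13)]/0.307, or about 3.4 to 3.5 points.

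This is lower than 4.1 because the gate sometimes opens for a reason unrelated to angina.

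**If any numerical difference counts**

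The gate is then almost always open and does no work.

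**Without the condition**

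The analysis is always reported, and the expected difference equals the true one.

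**The case against.** The strongest reply is that little is lost. The cost and resource comparison at 1, 2 and 3 years is unconditional. Angina is a powered secondary endpoint, and rehospitalization and revascularization are listed secondary endpoints. A reader will therefore see incremental cost and incremental events whatever happens. This is correct. It rules out a conclusion that a reader might draw, that the economic question is answered with bias or not at all; only the cost-effectiveness step is gated.

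Three other strong readings also go too far:

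- *That the analysis appears only when Absorb looks better.* The trigger is any difference between the arms, in either direction. Only the output, a cost of events avoided, suggests a favourable result.
- *That the reported effect is always exaggerated.* This needs a significance filter that the visible text does not state. Even with one, inflation is about 5% to 13% at a true 5 points. The background difference quoted in the trial rationale is larger still (27.9% − 16% = 11.9 points).
- *That the cost per event would be halved.* Hospitalizations and revascularizations generate cost, so the numerator can move with the denominator. The documents give no cost figure from which to work out the ratio.

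A definition of the trigger may lie in the redacted SAP text, so the plan cannot be faulted for lacking one. A definition would settle how the gate works, but it would not remove the dependence on results that the Protocol Summary states openly.

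Finally, a ratio is unstable when its denominator is near zero, which may be why the condition was written. That is a reason to report incremental cost and incremental effect separately with their joint uncertainty. It is not a reason to omit the analysis.

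**Conclusion.** The point holds as a minor one. The Protocol Summary makes the cost-effectiveness analysis depend on the observed event rates, and no visible text lifts that condition. The consequence is selective reporting of the cost per event avoided.

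The size depends on what *different* means. Under an assumed p<0.05 trigger, the gate opens by chance in about 10% to 14% of null trials at one time point. A true 2-point angina difference would appear as roughly 3.4 to 4.5 points, depending on the gate and the assumed rate. With true differences of 5 points or more the inflation is minor. If any numerical difference counts, the condition is empty.

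These figures rest on the assumed trigger, the assumed angina rates and, for the three-outcome gate, on independence and no effect on the other two outcomes. The endpoint is informational, and no primary or powered secondary test is touched.

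**What to change.** Delete the condition. State that incremental cost and incremental effect will be estimated jointly for named outcomes and time points whatever the event comparison shows, with joint uncertainty from, for example, a bootstrap of per-subject cost and effect. Report incremental cost and incremental effect separately alongside any ratio.

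Two details need a sentence each:

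- **Costing population.** Billing and claims data come from US sites only, so say whether the analysis is restricted to US subjects or how costs are assigned to the others.
- **Quality-adjusted time.** If EQ-5D is used for this, say how the 2-year point is interpolated, since no 2-year assessment is scheduled.

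If the sponsor prefers to keep a condition, define the trigger, outcomes and time points in advance and label the result as conditional on them.

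The cost is a wording change and modest extra analysis, with no new data collection. The downside is that the ratio may be imprecise when the effect is small, which the separate reporting of cost and effect addresses.

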1. INTRODUCTION

The ABSORB IV Randomized Controlled Trial (RCT) is designed to continue to evaluate the safety and effectiveness as well as the potential short and long-term benefits of Abbott Vascular Absorb™ Bioresorbable Vascular Scaffold (BVS) System⁴⁹, and the Absorb GT1™ BVS System, as compared to the commercially approved, control stent XIENCE. In the subsequent sections of this protocol, the term “Absorb BVS” will be used to represent both Absorb™ BVS and Absorb GT1™ BVS.

ABSORB IV is a prospective, randomized (1:1 Absorb BVS to XIENCE), single-blind, multi-center trial, registering approximately 2600 subjects from approximately 140 sites⁵⁰ in the United States and outside the United States. The primary objective of ABSORB IV is to evaluate 30-day and long-term clinical outcomes of the Absorb BVS compared to XIENCE in the treatment of subjects with ischemic heart disease caused by up to three *de novo* native coronary artery lesions in a maximum of two epicardial vessels, with a maximum of two lesions per epicardial vessel. The primary endpoint data of TLF through 30-day, tested for non-inferiority of Absorb BVS to XIENCE, will be tested on the ~2600 ABSORB IV subjects. The secondary objectives of ABSORB IV will be to evaluate TLF at 1-year and the incidence of angina occurring within 1 year, with treatment of Absorb BVS compared to XIENCE. The ABSORB IV protocol trial will compare patient reported outcomes, resource utilizations and costs between the Absorb BVS and XIENCE arms. These analyses will be based on all ~2600 subjects of ABSORB IV. The original design of the ABSORB IV trial also included an imaging ischemia sub-study aimed at providing the physiological and mechanistic evaluation of whether PCI treatment with Absorb BVS compared to XIENCE results in differences in myocardial ischemia in the early post-procedural period, and at 14 months and 62 months. However, this sub-study had to be stopped due to very slow enrollment (see **Section 12** for more details).

The enrollment/registration of ~2600 subjects in ABSORB IV will start after the completion of the enrollment/registration of 2000 primary analysis subjects in ABSORB III. All subjects in ABSORB IV will receive treatment of up to three *de novo* native coronary artery lesions in a maximum of two epicardial vessels, with a maximum two lesions in the same epicardial vessels with RVD ≥ 2.5 mm to ≤ 3.75 mm and lesion lengths ≤ 24 mm. All subjects will be screened per the protocol inclusion and exclusion criteria and all registered subjects will have clinical follow-up at 30, 90, 180, 270 days and 1, 2, 3, 4, and 5 years. In addition, all ~2600 subjects in ABSORB IV will complete patient-reported outcome self-administered questionnaires at baseline, 30, 180 days, and at 1 year. Additional PRO assessments may be conducted at 1, 3 and 5 years.

⁴⁹ The Absorb™ Bioresorbable Vascular Scaffold (BVS) System is the trade name for this product. During the course of development, multiple product names were used to describe this product including, Bioresorbable Vascular Scaffold (BVS) System, Bioabsorbable Vascular Stent, BVS Everolimus Eluting Coronary Stent System (EECSS), Abbott Vascular Bioabsorbable Device (AVBD) EECSS, BVS Cohort A (used in the ABSORB Cohort A trial) and BVS Cohort B (used in the ABSORB Cohort B trial).

⁵⁰ Majority sites in ABSORB IV also are participating sites in ABSORB III.

2. BACKGROUND INFORMATION

2.1.1 Name of the Investigational Device

The investigational device to be used in this trial is the Absorb BVS System⁵¹ and the Absorb GT1™ BVS System once it is commercially available. In this protocol, the investigational scaffold or test device is referred to as “the Absorb BVS”. The Absorb BVS System is manufactured by Abbott Cardiovascular Systems, Inc., California, an affiliate of Abbott Vascular, Inc.

2.1.2 Intended Indication

The Absorb Bioresorbable Vascular Scaffold (BVS) is a temporary scaffold that will fully resorb over time and is indicated for improving coronary luminal diameter in patients, including those with diabetes mellitus and acute coronary syndromes, with ischemic heart disease due to de novo native coronary artery lesions (length \leq 24 mm) with a reference vessel diameter of \geq 2.5 mm and \leq 3.75 mm.

2.1.3 Background Information

Please refer to **section 2.1.3 to 2.1.8** of ABSORB III Protocol ([REDACTED], August 16, 2018) for the detailed background information of the investigational device Absorb BVS, the control device XIENCE V, as well as the summary of pre-clinical and clinical studies.

2.1.4 Absorb GT1

Once Absorb GT1™ BVS System is commercially available, it can also be used in the ABSORB IV trial. The Absorb GT1 BVS System is composed of the following components:

- A bioresorbable poly(L-lactide) (PLLA) scaffold backbone
- A coating comprised of the active pharmaceutical ingredient everolimus and bioresorbable poly(D,L-lactide) (PDLLA)
- Four platinum marker beads, two each embedded at the proximal and distal ends of the scaffold for radiopacity
- An optimized delivery system (ODS) that leverages technology advancements of the XIENCE family of products, and incorporates design features from the Absorb BVS, XIENCE Xpedition®, and XIENCE Alpine delivery systems

The Absorb GT1 sizes are detailed in the table below.

⁵¹ The commercially approved CE marked device will be used in geographies where it is commercially available.

Table 2.1: Absorb GT1 BVS System Size Matrix

Scaffold Design	Product Diameter (mm)	Product Length (mm)				
		8	12	18	23*	28
Small	2.5	X	X	X	X	X
	3.0	X	X	X	X	X
Medium	3.5	N/A	X	X	X	X

* The commercially approved 23mm Absorb BVS GT1 device will not be used in ABSORB IV.

2.2 Trial Rationale

The Absorb BVS has been evaluated and continues to be evaluated in the ABSORB Family of Trials which includes ABSORB Cohort A and Cohort B, ABSORB EXTEND, ABSORB II and the ABSORB III Pivotal US trial. Retrospective comparison of Absorb BVS to XIENCE has demonstrated comparable TLF rates through 2 and 3 years (EXTEND 2-year TLF⁵²: 6.2% vs. 8.2%; Cohort B 3-year TLF⁵³: 9.9% vs. 11.4%). The potential long-term clinical benefit of Absorb BVS compared to metallic drug eluting stents has not been prospectively evaluated in randomized subject population.

Recurring angina has been associated with lifestyle limitations and worse self-reported quality of life, making the relief of symptoms one of the primary reasons for performing PCI⁵⁴. However, despite symptom relief with stenting, post-PCI angina recurrence is a clinically relevant burden that impacts patient’s quality of life. Recent retrospective descriptive comparison of Absorb BVS to XIENCE has shown preliminary evidence that Absorb BVS may be associated with lower rate of angina compared to XIENCE at 1 year (16% vs. 27.9%)⁵⁵. As Absorb BVS is a novel technology it will be important to evaluate the potential to reduce the recurrence of angina post PCI compared to existing DES technologies. The ABSORB IV trial will further evaluate the differences between Absorb BVS and XIENCE in the percentage of patients with angina after the stenting procedure, as determined by physician and/or research coordinator after interview of the patient, and as adjudicated by a clinical events committee (CEC).

3. TRIAL OBJECTIVE

ABSORB IV Primary Objective:

⁵² Whitbourn RJ. ABSORB EXTEND: An interim report on the 24-month clinical outcomes from the first 240 patients enrolled. TCT 2013.

⁵³ Serruys PW, Onuma Y, Garcia-Garcia H. First report of the three year clinical and multi-modality imaging results of the ABSORB trial evaluating the Absorb everolimus eluting bioresorbable vascular scaffold in the treatment of patients with De Novo native coronary artery lesions. ACC 2013.

⁵⁴ Holubkov R, Laskey WK, Haviland A, et al. Angina 1 year after percutaneous coronary intervention: a report from the NHLBI Dynamic Registry. *Am Heart J*. Nov 2002;144(5):826-833

⁵⁵ Stone GW. Demonstration of Clinical Superiority with a Bioresorbable Vascular Scaffold: The ABSORB IV Clinical Trial. <http://www.tctmd.com/show.aspx?id=120552>

- To evaluate 30-day clinical outcomes of the Absorb BVS compared to XIENCE in the treatment of subjects with ischemic heart disease caused by up to three *de novo* native coronary artery lesions in a maximum of two epicardial vessels, with a maximum of two lesions per epicardial
- To evaluate long-term clinical outcomes of the Absorb BVS compared to XIENCE in the treatment of subjects with ischemic heart disease caused by up to three *de novo* native coronary artery lesions in a maximum of two epicardial vessels, with a maximum of two lesions per epicardial vessel.

ABSORB IV Secondary Objectives:

- To evaluate 1-year clinical outcomes of the Absorb BVS compared to XIENCE in the treatment of subjects with ischemic heart disease caused by up to three *de novo* native coronary artery lesions in a maximum of two epicardial vessels, with a maximum of two lesions per epicardial
- To evaluate the incidence of angina occurring within 1 year with treatment of Absorb BVS compared to XIENCE.

